7.1 Definition of primary endpoint

CR of co-administered ivermectin-albendazole against *T. trichiura* is the primary endpoint in our study. Since treatment success is influenced by infection intensity, stratified block randomization will be used (baseline infection intensity: light infections and moderate/heavy infections) to ensure balanced treatment groups in terms of infection intensity.

7.2 Justification of number of trial subjects

Parallel group multi-country study

Based on available summarized efficacy measures from a recent review [1] and the published literature, we assume that the CR of albendazole against *T. trichiura* is 30% compared to 50% in the albendazole-ivermectin treatment regimen. To detect a difference with 90% power at a two-sided 5% significance level, we require 121 participants per study arm and 143 to account for potential loss to follow-up of 15%. We further assume the same treatment efficacy in the mid-term treatment and a 6-months reinfection risk of 10%. Consequently we expect a proportion of negative patients after 12 months of 44% in the albendazole arm and of 65% in the albendazole-ivermectin arm resulting in a required sample size of 111 participants per arm. To account for a loss to follow-up of 30% after 6 months and 40% at final assessment (12 months) we aim to recruit 300 participants in each treatment group (600 in total) in each country.

Subgroup analysis will be conducted stratifying the study population by age category (school-aged and adults). For the subgroup analysis we will pool the data from all 3 countries to ensure sufficient statistical power.

DF study

Since the existence of a drug effect is well known, the main aim of the study is the elucidation of the nature of the dose–response relationship. Modeling approaches showed that with 40 children enrolled in each of the 4 study arms (placebo, 200 μ g/kg, 400 μ g/kg, and 600 μ g/kg co-administered with albendazole (400 mg)) the dose response prediction model had a median precision (one half length of the 95%-confidence intervals) of 10% assuming associated cure rates of 2.5%, 50%, 60% and 70% taking into account a loss to follow up of 10%. The suggested sample size is also in line with the recommendations from *Klingenberg et al. 2009* [36]. This sample size is sufficiently high to determine the key PK parameters as well as pharmacokinetic/pharmacodynamic (PK/PD) relationships taking into account that PK variability is high.
Page 37 of 176

7.3 Description of statistical methods

The primary available case analysis will include all participants with primary end point data. In addition, an intention-to-treat analysis will be conducted considering all participants with missing endpoint data as treatment failure or all as treatment success to ensure that the results are not sensitive to potential loss to follow-up bias. CRs will be calculated as the percentage of egg-positive (larvae- positive for *S. stercoralis*) participants at baseline who become egg-negative (larvae-negative) after treatment. EPG will be assessed by adding up the egg counts from the quadruplicate Kato-Katz thick smears and multiplying this number by a factor of six. For *S. stercoralis* infection no further quantification of larvae in stool will be done. The ERR of STH infection will be calculated as:

$$ERR = 1 - \frac{\frac{1}{n}e^{\sum \log(EPG_{follow} - up + 1)} - 1}{\frac{1}{n}e^{\sum \log(EPG_{baseline} + 1)} - 1}$$

In the primary model we estimate the difference among CRs by using unadjusted logistic regressions. In a subsequent analysis an adjusted logistic regression (adjustment for age, sex and weight) will be performed.

Geometric mean egg counts will be calculated for the different treatment arms before and after treatment to assess the corresponding ERRs. Bootstrap resampling method with 5,000 replicates will be used to calculate 95% confidence intervals (CIs) for ERRs and the difference between the ERRs.

Results from the stool RDT for fecal occult blood will be categorized as negative, trace and positive. For calprotectin, individuals with levels exceeding 50 μ g/g will be considered as positive and concentrations be classified into low (51–149 μ g/g), medium (150–299 μ g/g) and high (\geq 300 μ g/g) intensity [16].

Anthropometric measurements such as height and weight of school-aged children will be translated into weightfor-age, height-for-age and weight-for-height related z-scores using readily available Stata macros calculating growth indicators for children 5-19 years [37]. Body mass index and indicators for muscle and fat tissue such as MUAC and skinfold thickness will serve as additional indicators of nutritional status for adults and will further be classified using a percentiles approach to compare within populations [38].

Questionnaires on physical functioning and treatment satisfaction will be evaluated by creating summary scores by summing up and transforming the single question scores according to the following formula: [(actual raw score-lowest possible raw score)/(possible raw score range)]*100 [25].

Nutritional and morbidity indicators will be analysed using logistic and linear regression as appropriate. To compare individual's changes in nutrition/morbidity categories as an effect from treatment McNemar's test will be applied. The analysis after 6 and 12 month of follow-up will be complemented by generalized estimating equation (GEE) models with independent correlation structure and empirical estimators to account for missing data.

AEs will be evaluated descriptively as the difference of proportion reporting AEs before and after treatment.

On the basis of the LC-MS/MS measurements, the following PK parameters for plasma will be calculated:

C_{max} maximal plasma concentration

 t_{max} time to reach C_{max}

Page 38 of 176

AUC area under the curve, from 0 to 24h and 0 to infinity

T_{1/2} elimination half-life

T and AUC above minimal inhibitory concentration (MIC)

 C_{max} and T_{max} will be observed values derived from the plasma concentration time profile. AUC and $T_{1/2}$ will calculated with the software WinNonlin (Version 5.2, Pharsight Corporation, USA) using compartmental analysis. The elimination half-life will be estimated by the equation: $T_{1/2} = \ln 2/\lambda$, where λ will be determined by performing a regression of the natural logarithm of the concentration values during the elimination period.

Further PK analysis will be undertaken fitting a structural compartmental PK model with the software NONMEM 7 [39] via nonlinear mixed effects modeling (allowing for both between patient variation and random effects). This model will describe the plasma drug levels in time, allowing one to investigate variation between patients in drug levels. In addition, PK/PD analysis will be undertaken via NONMEM to investigate the drivers of cure and/or burden reduction and potentially any covariates with drug levels.

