7.2 Justification of number of trial subjects

Based on available summarized efficacy measures from a recent review [1] and the published literature, we assume that the CR of albendazole against *T. trichiura* is 30% compared to 50% in the albendazole-ivermectin treatment regimen. To detect a difference with 90% power at a two-sided 5% significance level, we require 121 participants per study arm and 143 to account for potential loss to follow-up of 15%. We further assume the same treatment efficacy in the mid-term treatment and a 6-months reinfection risk of 10%. Consequently we expect a proportion of negative patients after 12 months of 44% in the albendazole arm and of 65% in the albendazole-ivermectin arm resulting in a required sample size of 111 participants per arm. To account for a loss to follow-up of 30% after 6 months and 40% at final assessment (12 months) we aim to recruit 300 participants in each treatment group (600 in total) in each country.

Subgroup analysis will be conducted stratifying the study population by age category (school-aged and adults). For the subgroup analysis we will pool the data from all 3 countries to ensure sufficient statistical power.

Page 155 of 176

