Questionnaires on physical functioning and treatment satisfaction will be evaluated by creating summary scores by summing up and transforming the single question scores according to the following formula: [(actual raw score-lowest possible raw score)/(possible raw score range)]*100 [23].

Nutritional and morbidity indicators will be analysed using logistic and linear regression as appropriate. To compare individual's changes in nutrition/morbidity categories as an effect from treatment McNemar's test will be applied. The analysis after 6 and 12 month of follow-up will be complemented by generalized estimating equation (GEE) models with independent correlation structure and empirical estimators to account for missing data.

AEs will be evaluated descriptively as the difference of proportion reporting AEs before and after treatment.

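### In three of the four protocols, independence-correlation GEE is said to account for missing data in the 6- and 12-month nutritional and morbidity analyses; it does not

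*Combined protocol and SAP*

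**What the plan says.** Section 7.3 of the original protocol opens its paragraph on these outcomes with "Nutritional and morbidity indicators will be analysed using logistic and linear regression as appropriate". It adds McNemar's test for within-person changes of category, and then complements the 6- and 12-month analysis with "generalized estimating equation (GEE) models with independent correlation structure and empirical estimators to account for missing data". The Côte d'Ivoire and Laos protocols carry the same sentence in section 7.3, and all three synopses repeat it. The Pemba protocol plans repeated-measures GEE models but names no working correlation and makes no statement about missing data.

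On the amount of loss, section 7.2 sets the recruitment target "To account for a loss to follow-up of 30% after 6 months and 40% at final assessment".

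Two other missing-data rules exist:

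- Section 7.3 has an analysis that counts missing results all as failures or all as successes. It is written under the primary available-case analysis, whose endpoint is at 14-21 days.
- The SAP provides for multiple imputation if missing data turn out well above its expected level of under 10%. Its Introduction limits the SAP to data collected 3 weeks after treatment, and its time and events table marks days 180, 185 and 360 as out of scope.

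**The concern.** A method is credited with a property that it lacks. The independence structure means that a person's earlier results contribute nothing to the estimate at a later visit. Empirical (sandwich) estimators make standard errors robust to within-person correlation, but they do not move a biased estimate. Logistic regression, linear regression and McNemar's test also use only people with the result in hand, so the GEE is the only step said to deal with loss at these visits.

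Section 4.3.2 refers the 6- and 12-month morbidity and nutrition comparisons to the repeated-measures analysis in section 7.3, so this sentence carries weight although it describes a complement. If loss relates to earlier health or infection status differently in the two arms, the between-arm estimate and its error rate are both wrong, while the protocol tells the reader that the matter is handled.

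**Working it through.** **1. The plan's own sample-size figures.** Inputs from section 7.2: the day-21 cure rate for albendazole "is 30% compared to 50% in the albendazole-ivermectin treatment regimen", "with 90% power at a two-sided 5% significance level", and a 6-month reinfection risk of 10%. With n = [p1(1−p1) + p2(1−p2)] × (1.960 + 1.282)² / (p1−p2)²:

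- Day 21: (0.21 + 0.25) × 10.507 / 0.20² = 120.8, so 121; 121/0.85 = 142.4, so 143. This matches "121 participants per study arm and 143 to account for potential loss to follow-up of 15"%.
- 12 months, proportion negative = [0.9c + (1−0.9c)c] × 0.9. For c = 0.30 this is 0.489 × 0.9 = 0.4401; for c = 0.50 it is 0.725 × 0.9 = 0.6525. Then n = (0.2464 + 0.2267) × 10.507 / 0.2124² = 110.2, so 111.

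All figures reproduce. With 40% loss, 120 of 300 are missing per arm and 180 remain, which gives about 98% power for 44% versus 65%. The allowance protects power. It does nothing about bias.

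**2. What independence GEE estimates.** With arm, visit and arm-by-visit terms, the estimating equations separate: in each arm-visit cell the residuals of the people observed must sum to zero, so the fitted value is the available-case mean. A check on simulated data gave a 12-month difference of 0.3436 (SE 0.1099) both from the GEE and from the plain comparison of those observed. Covariates would change the estimate, but would still not bring in earlier outcomes of people who were lost.

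**3. Size for a continuous indicator.** The documents give no SDs, correlations or loss mechanism for these indicators. Assumed: 300 per arm, within-person correlation 0.6, 40% loss at 12 months, no true effect, and loss related to earlier values with log-odds of 0.5 to 1.0 per SD where it is outcome-dependent.

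| Loss pattern | Bias in contrast | Type I error |
|---|---|---|
| Same pattern in both arms | none | about 5% |
| One arm only; 30% already lost at random by month 6, the rest following the 6-month value | about 0.04-0.08 SD | 7-12% |
| One arm only; all the loss follows earlier values | about 0.11-0.22 SD | 20-54% |

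The error rates agree with a hand approximation. The SE of the contrast is about √(2/180) = 0.105 SD. A bias of 0.04 gives Φ(0.38−1.96) + Φ(−0.38−1.96) = 0.07. A bias of 0.08 gives 0.12, 0.11 gives 0.18, and 0.22 gives 0.55.

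**4. The same mechanism on the protocol's infection path.** This outcome lies outside the GEE sentence's stated subject, but it is the one for which the protocol gives rates. Assume 40% loss in each arm, with loss in the albendazole arm twice as high among those not cured at day 21.

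- Loss is 0.4/(0.3 + 0.7×2) = 0.235 among the cured and 0.471 among the uncured.
- Expected 12-month negativity is 0.837 after day-21 cure and 0.27 otherwise.
- The observed proportion is (0.3×0.765×0.837 + 0.7×0.529×0.27)/0.6 = 0.487 instead of 0.440.
- The difference becomes 65.25 − 48.7, about 16.6 points, against a true 21.2. In simulation, coverage of the 95% interval was about 85%.

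With the same doubling in both arms the difference is 21.1, although each arm's proportion is off by 4 to 5 points. Standardising to the observed day-21 result gave 21.1-21.3 in every scenario run, so the information needed is already collected.

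**The case against.** The case on the other side has several sound parts.

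- **Reach.** A reader might infer that all 6- and 12-month results, prevalence included, rest on this sentence. The documents do not support that. It stands in the nutrition and morbidity paragraph, prevalence is not named, the GEE is a complement, and Pemba lacks the wording. Section 4.1 of the three protocols that have the sentence lists these indicators as exploratory endpoints.
- **Theory.** It would be too strong to say that the method needs loss completely at random. It is also consistent when loss depends only on covariates in a correct model. The model is not specified, and section 4.3.1 collects household data for later adjustment. Adjustment could therefore help, but not where loss follows earlier outcomes.
- **Intent.** The phrase may mean only that people with incomplete visits stay in the analysis with robust standard errors. That is possible, but the words say more.
- **Size.** A reader might take an error rate near 50% as the expected consequence. It is an extreme: all the loss must follow earlier values in one arm only, and participants, treating staff and outcome assessors are blinded. Since 30% loss is allowed by month 6, under monotone dropout only 10 of the 40 points could follow an observed 6-month value.
- **Amount.** The 30% and 40% are sample-size allowances, not observed or predicted differential loss.

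These points narrow the finding. They do not supply a missing-data method for days 180 and 360.

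**Conclusion.** Wrong as written, within limits. In the original, Côte d'Ivoire and Laos protocols, the complementary 6- and 12-month analysis of nutritional and morbidity indicators is given a missing-data property that it does not have, at visits where 30-40% loss is allowed for and no other rule applies. That conclusion follows from the method and does not depend on the simulations.

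The size does depend on assumptions outside the documents. It ranges from no bias in the contrast under a common loss pattern to about 0.2 SD if all the loss follows earlier values in one arm only. The day-21 primary analysis is not touched. The point should be corrected before the later visits are analysed, but it does not threaten the trial's main conclusion.

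**What to change.** Delete the statement that this GEE accounts for missing data. In the plan for days 180 and 360, which the present SAP does not cover:

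1. State the missingness assumption for each visit, and report loss by arm and by earlier status.
2. Use a method valid under missing at random that draws on earlier observed outcomes. Options are GEE after multiple imputation, inverse-probability-weighted GEE, or a likelihood-based mixed model with arm, visit, arm-by-visit and baseline value.
3. Add a sensitivity analysis under missing not at random.

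No new data are needed, because the earlier visits are already collected. The cost is wording and a modest amount of analysis. The result would still rest on missing at random, which cannot be verified but is a weaker assumption than the present one.

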Sample size	1960 (600 participants in each of 3 settings for the parallel group trial including 160 participants for the dose-finding (DF) study)				
Indication	Trichuris trichiura infection (eggs in stool)				
Investigational Product and Reference Treatment	Ivermectin and albendazole				
Study Rationale	To provide evidence on				
	a) potentially enhanced efficacy by combining the standard drug albendazole with ivermectin in school-aged children and adults against infection with T. trichiura .				
	b) effective doses of ivermectin in combination with albendazole in school- aged children against infection with T. trichiura .				
Study Objectives	To compare the efficacy and safety of: (a) standard doses of co-administered ivermectin (200 μ g/kg) and albendazole (400 mg) compared to albendazole (400 mg) monotherapy in community members aged 6-60 years and (b) ascending doses of ivermectin ((i) 200 μ g/kg, (ii) 400 μ g/kg, and (iii) 600 μ g/kg) co-administered with albendazole (400 mg) in school-aged children (6-12 years) infected with T. trichiura and to measure ivermectin and albendazole disposition in children using a microsampling device.				

Our primary objective is to comparatively assess the efficacy in terms of cure rates (CRs) against T. trichiura infections among school-aged children and adults of the following oral treatment regimens:					
a) in a parallel group trial:					
Albendazole (400 mg)/ivermectin (200 µg/kg) combination					
Albendazole (400 mg) monotherapy					
b) in the DF study (school-aged children only):					
Albendazole (400 mg)/ivermectin (200 µg/kg) combination					
Albendazole (400 mg)/ivermectin (400 µg/kg) combination					
Albendazole (400 mg)/ivermectin (600 µg/kg) combination					
Placebo					
The secondary objectives of the trial are:					
a) To evaluate the safety and tolerability of the treatment regimens					
b) To compare the egg reduction rate (ERR) of the treatment regimens					
(combination vs. monotherapy and ascending doses of the combination) against T triching					
c) To determine the CRs and ERRs of the drugs in study participants (6-					
60 years) infected with hookworm, Ascaris lumbricoides and					
Strongyloides stercoralis					
d) To investigate potential extended effects on follow-up helminth					
prevalences (6 and 12 months post-treatment) of the two standard-dose					
treatment regimens (as assessed among participants with cleared infection on days 21 and 180)					

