6.1 Adverse event definitions

The term "adverse event" could include any of the following events which develop or increase in severity during the course of the study, after administration of the study product:

a) Any unfavorable and unintended signs, symptoms or disease temporally associated with the use of a medicinal product, whether or not considered related to the condition under study and the study product;

b) Any abnormality detected during physical examination.

The medical conditions present at the initial trial visit that do not worsen in severity or frequency during the trial will not be defined as AEs but be considered baseline medical conditions. For the purpose of this trial, disease progression and relapse will be considered as treatment failure, not as an AE.

The observation time for AEs starts when the treatment is initiated until day 21 (3 weeks after last drug administration).

These data will be recorded on the appropriate case report form (CRF) sections, regardless of whether they are thought to be associated with the study or the drug under investigation. Associated with the use of the drug means that there is a reasonable possibility that the event may have been caused by the drug (see also relatedness definitions below).

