6.1 Adverse event definitions

The term "adverse event" could include any of the following events which develop or increase in severity during the course of the study, after administration of the study product:

a) Any unfavorable and unintended signs, symptoms or disease temporally associated with the use of a medicinal product, whether or not considered related to the condition under study and the study product;

b) Any abnormality detected during physical examination.

The medical conditions present at the initial trial visit that do not worsen in severity or frequency during the trial will not be defined as AEs but be considered baseline medical conditions. For the purpose of this trial, disease progression and relapse will be considered as treatment failure, not as an AE.

The observation time for AEs starts when the treatment is initiated until day 21 (3 weeks after last drug administration).

These data will be recorded on the appropriate case report form (CRF) sections, regardless of whether they are thought to be associated with the study or the drug under investigation. Associated with the use of the drug means that there is a reasonable possibility that the event may have been caused by the drug (see also relatedness definitions below).

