If, after database lock, deviations or additional analyses are required to supplement the planned analyses described in this SAP, those will not be described in an amended SAP, but they will be identified in the related publication.

This SAP has been written in consideration of the following guidelines:

- International Conference on Harmonization (ICH) E9, Guidance for Industry: Statistical Principles for Clinical Trials (ICH E9 1998)1
- ICH E3, Guidance for Industry: Structure and Content of Clinical Study Reports (ICH E3 1995)

Statistical analysis will be done using R 5.3.1 on a Windows 64 bit system.

Page 167 of 176

Study Objectives and Endpoints

Study Objectives

Primary Objective

To assess the efficacy and safety of standard doses of co-administered ivermectin (200 μ g/kg) and albendazole (400 mg) against *Trichuris trichiura* compared to albendazole (400 mg) alone in community members aged 6-60 years.

Secondary Objectives

To evaluate the safety and tolerability of the treatment regimens

To compare the egg reduction rate (ERR) of the treatment regimens against T. trichiura

To determine the CRs and ERRs of the drugs in study participants (6-60 years) infected with hookworm, *Ascaris lumbrico*ides and *Strongyloides stercoralis*

Study Endpoints

Primary

T. trichiura cure rate (CR) defined as infection status assessed by Kato-Katz 14-21 days after treatment expressed as cure rate, i.e. conversion from being egg positive pre-treatment to egg negative post-treatment.

Secondary

ERR against T. trichiura

CRs and ERRs against A. lumbricoides, hookworm and S. stercoralis

Adverse events

Infection status assessed by PCR

Safety

Statistical Hypotheses

Primary hypothesis: albendazole-ivermectin has a higher efficacy against *T. trichiura* infections compared to albendazole alone.

Study Design

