	treatment					
	After treatment					
Cure rat	e, %					
N partic	ipants cured (%)					
	From light infection					
	From moderate infection					
	From heavy infection					
Geometric mean EPG						
	Before treatment					
	After treatment					
Egg-red	uction rate, %					
S. sterce	oralis ^a					
No. of p infection	participants positive	for				
	Before treatment					
	After treatment					
Cure rat	e, %					

EPG: eggs per gram of stool

^a S. stercoralis infection was assessed qualitatively only (positive vs negative) in stool samples collected in Lao PDR

Page 175 of 176

Safety analysis

Adverse events will be analysed descriptively and summarized (for each country) as outlined in the 2 tables below.

Table: Adverse events assessed at baseline, 3 hours and 24 hours post treatment by treatment arm

	Before treatment	3h post treatment	24h post treatment	After 24h
ALB				
Total participants assessed				
Participants with AE				
% participants with AE				
Number of AEs				
IVM-ALB				
Total participants assessed				
Participants with AE				
% participants with AE				
Number of AEs				
TOTAL				
Total participants assessed				
Participants with AE				
% participants with AE				
Number of AEs				

Page 176 of 176

	Baseline					3h post-treatment					24h post-treatment							
	AL	B	IVN	1-	ΤΟ	ГА	AL	B	IVN	1-	TO	FAL	AL	B	IVN	1-	тот	AL
			ALI	B	L				ALI	3					ALI	B		
Adver	N	N	N	N	N	N	N	N	N	Ν	N	N	N	N	N	N	N	N
se	A	Gr	A	Gr	A	Gr	A	Gr	A	Gr	An	Gr	A	Gr	A	Gr	An	Gr
event	nv	ad	nv	ad	nv	ad	nv	ad	nv	ad	v	ad	nv	ad	nv	ad	v	ad
event	gr	e	gr	e	gr	e	gr	e	gr	e	gr	e	gr	e	gr	e	gra	e
	ad	>2	ad	>2	ad	>2	ad	>2	ad	>2	ad	>2	ad	>2	ad	>2	de	>2
	e		e		e		e		e		e		e		e		au	
							-		-		-		-		-			
Heada																		
che																		
Abdo																		
minal																		
pain																		
Itching																		
Nause																		
а																		
Vomiti																		
ng																		
Diarrh																		
ea																		
Fever																		
Allergi																		
C																		
reactio																		
n																		
11																		
Other																		

Table: Specific adverse events by treatment arm and time point

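### The protocols' before-after rule for adverse events conflicts with their own AE definition, and the SAP tables that replace it state no counting rule, no between-arm estimate and no type or grade for events after 24 h

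*Combined protocol and SAP*

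**What the plan says.** **Protocol rule.** Section 7.3 of the Swiss (EKNZ), Pemba, Côte d'Ivoire and Laos protocols carries the same sentence: "AEs will be evaluated descriptively as the difference of proportion reporting AEs before and after treatment". It names no arm, estimate or interval.

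**Protocol definition.** Section 6.1 limits AEs to events "which develop or increase in severity during the course of the study, after administration of the study product". Conditions already present at the initial visit "that do not worsen in severity or frequency during the trial will not be defined as AEs" and are treated as baseline medical conditions.

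**Objectives.** The synopsis of the Swiss protocol sets the aim as "To compare the efficacy and safety of: (a) standard doses" of the combination against albendazole monotherapy. The SAP's Primary Objective begins "To assess the efficacy and safety of standard doses of co-administered ivermectin" and also names albendazole alone as the comparator.

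**SAP rule.** The Safety analysis section says: "Adverse events will be analysed descriptively and summarized (for each country) as outlined in the 2 tables below".
- Table 1 ("Table: Adverse events assessed at baseline, 3 hours and 24 hours post treatment by treatment arm") has blocks for ALB, IVM-ALB and the total. Each gives the number assessed, the number and percentage with an AE, and the number of AEs. The columns are before treatment, 3 h, 24 h and after 24 h.
- Table 2 ("Table: Specific adverse events by treatment arm and time point") lists specific AEs by arm, for any grade and for grade above 2, at baseline, 3 h and 24 h.

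**Collection.** Participants are asked about symptoms before dosing (4.3.1) and about AEs at 3 h, 24 h and 3 weeks (6.2).

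**The concern.** Under the section 6.1 definition no AE can exist before treatment. The first term of the section 7.3 difference is therefore the prevalence of baseline symptoms, and subtracting it credits the regimen with every complaint that cleared. A participant who is symptomatic at both times contributes nothing, even if the symptom worsened, although section 6.1 counts worsening as an AE. Following that sentence literally could yield little or no AE burden when new events did occur.

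The SAP avoids the subtraction but leaves three gaps:
- It does not say how post-dose events relate to the pre-treatment record.
- It gives no estimate for a safety comparison that the objectives describe as comparative.
- The only table with type and grade stops at 24 h, although AEs are collected to day 21.

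**Working it through.** The documents state no AE rate, safety power or safety precision, so there is no safety figure to reproduce. The only related design figure is the primary sample size, and it reproduces: (1.960 + 1.282)² × (0.3×0.7 + 0.5×0.5) / 0.2² = 120.8, so 121 per arm; 121/0.85 = 142.4, so 143. The SAP anticipates 143 per arm and the protocols plan 300 per arm in each country. Both are used below. All symptom and AE rates are assumptions.

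**1. What the protocol difference measures.** Let b be the proportion symptomatic before dosing, r the share of those who resolve, and t the proportion of all participants with a new event (arising among the symptom-free).
- After = b(1 − r) + t.
- After − before = t − b·r.
- With b = 0.20, r = 0.50, t = 0.10: after = 0.10 + 0.10 = 0.20, so the difference is 0. Yet 10% of all participants (0.10/0.80 = 12.5% of the symptom-free) have a new event.
- The difference is 0 whenever t = b·r. For b from 0.10 to 0.30 and r from 0.25 to 0.75, t runs from 0.10×0.25 = 2.5% to 0.30×0.75 = 22.5%.

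**2. What the SAP tables show.** They print a percentage at each time with no subtraction, so their content depends on the unstated counting rule. If post-dose cells hold only events new or worse than baseline, nothing cancels. If they hold every symptom present, resolution can still mask an excess. An illustration of that second reading, with 300 per arm:

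| | Before | Resolved | New | After |
|---|---|---|---|---|
| ALB | 60 | 30 | 12 | 42 (14%) |
| IVM-ALB | 60 | 45 | 30 | 45 (15%) |

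- Before-after change: −6 points and −5 points.
- Post-dose percentages: difference 1.0 point, SE = √(0.14×0.86/300 + 0.15×0.85/300) = 0.0287, 95% CI −4.6 to 6.6.
- New events, 4% against 10%: difference 6.0 points, SE = √(0.04×0.96/300 + 0.10×0.90/300) = 0.0207, 95% CI 1.9 to 10.1.

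This example needs different resolution in the two arms (50% and 75%). It shows why the counting rule matters and does not predict the result.

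**3. Precision of a between-arm risk difference.** The Wald half-width with the same rate p in both arms is 1.96 × √(2p(1 − p)/n). For p = 0.10 and n = 300: 1.96 × √(0.18/300) = 4.8 points.

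| Assumed rate in both arms | 5% | 10% | 20% | 30% |
|---|---|---|---|---|
| 143 per arm | ±5.1 | ±7.0 | ±9.3 | ±10.6 |
| 300 per arm | ±3.5 | ±4.8 | ±6.4 | ±7.3 |

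**4. Follow-up coverage.** AEs are sought at 3 weeks. Table 1 has a column after 24 h, with totals only. Table 2 has none, so events first reported at the 3-week visit have no planned display by type or grade.

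**The case against.** The SAP is the later analysis document and does no subtraction. In the first example its Table 1 would show 20% before and 20% after, or 10% after if the section 6.1 definition is applied. It would not show 0. Both tables set the arms side by side with counts and Table 1 gives denominators, so a risk difference for any AE can be worked out from it. Descriptive AE reporting is common. The SAP's secondary safety objective is to evaluate, its only stated hypothesis concerns efficacy, and the trial is not sized for safety.

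Most of this stands, and it rules out some stronger readings that a reader might draw:
- **That the SAP nets new events against resolved ones.** It does not. The cancelling belongs to the protocol sentence.
- **That the SAP tables count every symptom present after dosing.** This is an inference. The rows refer to AEs, and section 6.1 would restrict those to new or worsened events. The pre-treatment AE column shows the term being used more loosely, so the rule is unclear but not demonstrably wrong.
- **That the arms cannot be compared, or that late events go unreported.** Informal comparison is possible, and Table 1 includes late totals by arm.

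The objection does not rescue the protocol sentence, which contradicts section 6.1. Nor does it explain why the SAP replaces that sentence silently, when its Introduction says substantial differences from the protocol will be identified. A risk difference with an interval is itself descriptive and needs no claim of power.

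**Conclusion.** The protocol rule is wrong as written: it conflicts with the AE definition in the same documents and can return 0 when participants have had new events. Over the assumed range (10–30% symptomatic at baseline, 25–75% of them resolving), a difference of 0 is compatible with new events in 2.5% to 22.5% of participants. These rates are illustrative, because the documents give none.

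For the SAP tables this is a cheap improvement, not an error. They need a stated counting rule, an estimate with an interval to match the comparative objectives, and late events by type and grade. Nothing in the documents shows that the SAP output would conceal a real safety difference. The weakness lies in a descriptive secondary analysis and leaves the primary cure-rate comparison untouched.

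**What to change.** In the SAP's Safety analysis section:

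1. Withdraw the before-after difference explicitly, and record this as a departure from section 7.3 of the protocols.
2. Define the post-dose count as participants with at least one event new or worse than their own pre-treatment symptom record. Show pre-treatment symptoms separately, labelled as baseline.
3. For each country, report the between-arm risk difference with 95% CI for any AE and for grade above 2, as descriptive estimates with no power claim. The melded binomial interval already specified for cure rates could be reused, which helps if grade above 2 events are sparse.
4. Add a column from after 24 h to day 21 to the specific-AE table.

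The cost is SAP wording, revised table shells and a little more programming. Symptoms before dosing and AEs to day 21 are already collected, so no visit or data item is added. The downside is that the intervals will be fairly wide, especially at 143 per arm, and should be presented as such.
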